**Table 16. Potentially Clinically Significant Values for 12-Lead ECG Parameters**

12-Lead ECG	Units	Criteria for PCS Values (Observed values)		Criteria for PCSC values (Change from Baseline)	
		High	Low	Increase	Decrease
QTcF	msec	>450 but $\leq$ 480 >480 but $\leq$ 500 >500	NA	$\geq$ 30 to 60 >60	NA

#### 8.4.4. Vital Signs

Vital signs will include oral temperature(°C), respiratory rate (breaths per minute), heart rate (beats per minute [bpm]), and blood pressures (mmHg). Heart rate and blood pressure were collected in supine position and standing position at all scheduled time points.

Vital sign results and mean changes from baseline will be summarized by scheduled visit. It will also include the summary of last values on treatment and on study assessments.

Potentially clinically significant values as outlined in the table below will be summarized by treatment and for anytime on treatment, last value on treatment, within 28 Days after the last dose of treatment (follow-up period). By-participant listing of vital signs will also be provided.

**Table 17. Potentially Clinically Significant Values for Vital Sign Parameters**

Vital Sign	Units	Criteria for PCS Values (Observed values)		Criteria for PCS values (Change from Baseline values)	
		High	Low	Increase	Decrease
Heart rate (supine and standing)	Beats/min	>120	<40	NA	NA
Respiratory Rate	Breaths/min	>20	<8	NA	NA
Systolic blood pressure (supine and standing)	mmHg	>180	<90	$\geq$ 30	$\geq$ 30

Vital Sign	Units	Criteria for PCS Values (Observed values)		Criteria for PCS values (Change from Baseline values)	
		High	Low	Increase	Decrease
Diastolic blood pressure (supine and standing)	mmHg	>110	<50	≥20	≥20
Supine – Standing Systolic Blood Pressure	mmHg	≥20			
Supine – Standing Diastolic Blood Pressure	mmHg	≥10			
Orthostatic hypotension: supine – standing SBP and DBP	mmHg	SBP ≥20 and DBP ≥10			
Possible orthostatic hypotension: supine – standing SBP and DBP	mmHg	SBP ≥20 or DBP ≥10			

#### **8.4.5. Physical Examination**

[figure not shown]
A full physical examination is to be conducted during Screening and at Day 112. At other visits, physical examinations will include a brief assessment of general appearance, cardiovascular, respiratory, gastrointestinal, and neurological systems and followed by a targeted physical assessment as needed. A by-participant listing of physical examination findings will also be provided.

### 8.4.6.

A horizontal bar chart illustrating the distribution of 1000 random numbers. The x-axis represents the value of the random numbers, ranging from 0 to 1. The y-axis represents the frequency of each value, with 100 bars displayed. The distribution is approximately uniform, with most values falling between 0.4 and 0.6. The bars are black and have thin white outlines.

### 8.4.7.

A large rectangular area of the page is completely blacked out, indicating that the original text has been removed or is not to be disclosed.

#### **8.4.8. Other Safety Analysis**

Not applicable.

#### **8.5.**

## **9. SUMMARY OF INTERIM AND DMC ANALYSES**

Not applicable.

## 11. LIST OF APPENDICES

APPENDIX A. SCHEDULE OF ASSESSMENTS

APPENDIX B. DETAILS OF STATISTICAL METHODOLOGY

APPENDIX C. HANDLING OF MISSING DATES

APPENDIX D. ANTIDOPAMINERGIC MEDICATIONS

APPENDIX E. HI-DEF SCORING INSTRUCTIONS

## APPENDIX A. SCHEDULE OF ASSESSMENTS

Assessments	Screening Period		Treatment Period					Follow-Up	
	Days -28 to -2	Day -1	Day 1	Day 14 ( $\pm 2$ days)	Day 28 ( $\pm 2$ days)	Day 56 ( $\pm 2$ days)	Day 84 ( $\pm 2$ days)	Day 98 ( $\pm 2$ days)	Day 112 ( $\pm 2$ days) or ET
Informed consent a	X								
Inclusion/exclusion criteria	X	X	X						
Family/Medical history and demographics b	X	X							
Participant training c	X	X							
Body weight	X		X		X	X	X		X
Body height	X								
Vital signs (including orthostatics) d	X		X	X	X	X	X	X	X
Physical examination e	X				X		X		X
CAG test f (if not collected as part of medical history)	X								
FSH test g	X								
Serology test h	X								
12-lead ECG i	X				X		X		X
Clinical laboratory assessments j	X		X		X		X		X
Urine drug test	X		X	X	X	X	X	X	X
Alcohol test k	X		X	X	X	X	X	X	X
Cigarette/tobacco use assessment l	X		X	X	X	X	X	X	X
Pregnancy test m	X		X		X		X		X

Assessments	Screening Period		Treatment Period					Follow-Up	
	Days -28 to -2	Day -1	Day 1	Day 14 ( $\pm 2$ days)	Day 28 ( $\pm 2$ days)	Day 56 ( $\pm 2$ days)	Day 84 ( $\pm 2$ days)	Day 98 ( $\pm 2$ days)	Day 112 ( $\pm 2$ days) or ET
C-SSRS (Screening/Baseline)	X								
UHDRS p	X						X		
Montreal Cognitive Assessment	X								
Global Impression – Severity q	X						X		
Cognitive battery r	X								
Hi-DEF Scale							X		

Assessments	Screening Period		Treatment Period					Follow-Up	
	Days -28 to -2	Day -1	Day 1	Day 14 ( $\pm 2$ days)	Day 28 ( $\pm 2$ days)	Day 56 ( $\pm 2$ days)	Day 84 ( $\pm 2$ days)	Day 98 ( $\pm 2$ days)	Day 112 ( $\pm 2$ days) or ET
Randomization			X						
IP self-administration v				X (once daily in the morning)					
IP dispensation w			X	X	X	X			
IP Adherence x				X					
IP Accountability/Return y			X	X	X	X	X		
AEs/SAEs				X (from time of ICF throughout the duration of participation)					
Prior and concomitant medications				X					

Abbreviations: AE = adverse event, COVID-19 = coronavirus disease 2019; C-SSRS = Columbia–Suicide Severity Rating Scale; ECG = electrocardiogram; ET = early termination; FSH = follicle-stimulating hormone; HD = Huntington’s Disease; Hi-DEF = Huntington’s Disease Everyday Functioning Scale; HIV = human immunodeficiency virus; ICF = informed consent form; IP = investigational product; [REDACTED]; [REDACTED]; [REDACTED]; SAE = serious adverse event; UHDRS = Unified Huntington’s Disease Rating Scale.

Note: [REDACTED]

- Both participants and study partners (if applicable) will be consented during the Screening Period. [REDACTED]
- In addition to full medical history, all medications and supplements taken within 8 weeks prior to Screening, all medications used to treat HD regardless of timing, and all nonpharmacological methods (eg, psychosocial, psychotherapeutic) used to treat or prevent neuropsychiatric, functional, and cognitive manifestations of HD are to be recorded. Information regarding diagnosis, isolation, and/or hospitalization due to COVID-19 will be documented as part of medical history, AE collection, and prior/concomitant medication/procedure collection at screening and throughout the study. Confirmed (genetically tested) or suspected family history of HD will be collected.
- Participants and study partners (if applicable) will be trained by study staff on the use of software applications and devices necessary for the conduct of the study.

- d. Vital signs to include body temperature, respiratory rate, heart rate, and blood pressure. On dosing days, vital signs will be measured prior to dosing. Blood pressure and heart rate will be measured after the participant has been in the supine position for at least 5 minutes and then repeated approximately 1 and 3 minutes after standing at all scheduled time points. Vital signs can be repeated once per visit if out of range.
- e. A full physical examination is to be conducted during Screening and at Day 112. At other visits, physical examinations will include a brief assessment of general appearance, cardiovascular, respiratory, gastrointestinal, and neurological systems and followed by a targeted physical assessment as needed. A symptom-directed examination may be conducted at any time at the discretion of the investigator.
- f. Test results of genetically confirmed disease with CAG expansion  $\geq 36$  collected as part of medical history is acceptable in lieu of central laboratory confirmation. For any genetic counseling, the study sites should follow the local practice.
- g. Serum FSH test will be conducted at Screening for the female participants to confirm whether a female participants with  $\geq 12$  months of spontaneous amenorrhea meets the protocol-defined criteria for being postmenopausal.
- h. To include hepatitis B and C screening tests, HIV-1 and -2 antibody.
- i. Single ECG will be measured after the participant has been in the supine position for at least 5 minutes. When ECG measurements coincide with safety assessments, vital signs assessment or blood draws, blood draws should be carried out after ECG and vital signs.
- j. Clinical laboratory assessments will include blood samples for hematology, clinical chemistry, biochemistry, coagulation, serology, genetic testing, and urinalysis. Samples will be collected  $\leq 2$  hours prior to dosing on dosing days. On non-dosing days, collection may occur at any time.
- k. A breath test for alcohol will be performed.
- l. Data on cigarette use will be collected using the question: "How many packs of cigarettes did you smoke over the past 7 days?" at the time points specified.
- m. Serum pregnancy tests will be conducted for all female participants at Screening; urine pregnancy tests will be conducted at other scheduled time points for female participants that are not postmenopausal or permanently sterile.

■ [REDACTED]  
■ [REDACTED]  
■ [REDACTED]  
■ [REDACTED]  
p. [REDACTED]. Independence Scale will be conducted at Screening, and on Days -1, 28, 84 and 112.

■ [REDACTED]  
■ [REDACTED]  
r. Cognitive tests at all time points are to be performed at the same time of day ( $\pm 2$  hours) and postdose on dosing days. [REDACTED]  
■ [REDACTED]  
■ [REDACTED]  
■ [REDACTED]  
■ [REDACTED]

- [REDACTED]
- [REDACTED]
- v. On visit Days 1, 14, 28, 56, and 84, participants will self-administer IP in the clinic under the supervision of study staff. All scheduled safety assessments will be conducted prior to dosing and all scheduled cognitive tests will be administered post dosing.
- w. Study staff will dispense enough IP for the participant to take daily at home until the next scheduled visit.
- x. IP administration will be monitored using the [REDACTED]. Participants will complete the training within the application. Thereafter participants should use the application each time they take IP and sites should regularly use the dashboards to follow up on instances of non-adherence with IP. IP adherence will not be captured after participants discontinue IP.
- y. Participants will bring all used packaging and unused IP to the clinic at each visit for study staff to review and document.

## APPENDIX B. DETAILS OF STATISTICAL METHODOLOGY

### Sample SAS Code for MMRM

```
proc mixed data=data method=ml;
  class trtp(ref="Placebo") avisit usubjid ;
  model chg = trtp avisit trtp*avisit base /ddfm=kr;
  repeated avisit / subject= usubjid type=UN r;
  lsmeans trtp*avisit / diff=all cl alpha=0.05;
  ods output diffs=lsdiffs lsmeans=lsmeans ConvergenceStatus=cs;
run;
```

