## 5.2. Sample Size and Study Power

The study is designed to detect a difference between placebo and the SAGE-718 group in the change from baseline to Day 84 for the primary endpoint, SDMT score. Using a 2-sided test at an alpha level of 0.05, a sample size of approximately 71 evaluable participants per treatment group would provide 90% power to detect a difference of 4 points between SAGE-718 and placebo arms in the change from baseline to Day 84 in SDMT values, assuming that the SD of the change from baseline in SDMT is 7.3 points.

Assuming a 20% dropout and a 1:1 randomization ratio, approximately 178 randomized participants (89 per treatment group) will be required to obtain 71 evaluable participants per treatment group. Evaluable participants are defined as those randomized participants who receive IP and have a valid baseline and at least 1 postbaseline SDMT assessment.

Additional participants may be randomized to ensure a sufficient number of evaluable participants or if the dropout rate is higher than 20%.

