- 5) The population summary level deals with the difference between SAGE-718 and placebo treatments in mean change from baseline to Day 84 in Symbol Digit Modalities Test (SDMT) The primary efficacy endpoint is the change from baseline to Day 84 on the SDMT score. This primary endpoint will be analyzed using a mixed-effects model for repeated measures (MMRM). The model will include baseline SDMT score as a continuous explanatory variable, treatment, assessment time point, and time point-by-treatment as categorical explanatory variables. The Kenward-Roger correction to degrees of freedom will be applied. All explanatory variables will be treated as fixed effects in the model. All post-baseline time points will be included in the model. An unstructured (UN) covariance matrix with the default Newton-Raphson optimization algorithm as implemented in the SAS procedure PROC MIXED will be used to estimate the within-subject correlation. If this model fails to converge, the Fisher Scoring algorithm (via the SCORING option of the PROC MIXED statement), the no-diagonal factor analytic structure (via the TYPE=FA0( $T$ ) option of the REPEATED statement, where  $T$  is the total number of time points), Toeplitz, Autoregressive (1) [AR (1)], Compound symmetry (CS) covariance structure will be used, following this sequence until convergence is achieved. If the model still does not converge with CS structure, the Glimmix procedure with option of parametrizing UN to Cholesky root matrix will be used and in the case it also does not converge no results will be reported. When the covariance structure is not UN, the sandwich estimator for the variance-covariance matrix will be derived, using the EMPIRICAL option in the PROC MIXED statement in SAS. The primary comparison will be between SAGE-718 and placebo at the Day 84. Least squares means and 95% confidence interval will be summarized, and the p-value from the hypothesis test of no difference between the treatment groups will be also presented.

A plot showing the LS means of SDMT score  $\pm$  SE bar over time within each treatment group will be provided.

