#### 8.3.3.4. Subgroup Analyses of Primary Analysis

Primary endpoint will be analyzed for the following subgroups:

- Age ( $\leq 50, > 50$ )
- Sex (Male, Female, Unknown/Undifferentiated)
- BMI ( $\leq 18.4, 18.5-24.9, 25-29.9, \geq 30 \text{ kg/m}^2$ )
- Country (US, Rest of World)
- Baseline MoCA score ( $< 18, \geq 18$ )
- Baseline UHDRS – Independent scale ( $< 80, \geq 80$ )
- CAP ( $< 100, \geq 100$ )
- [REDACTED]
- [REDACTED]
- [REDACTED]
- Baseline Symbol Digit Modalities Test (SDMT) ( $< M, \geq M$ , where M-Mean value at Baseline in FAS)
- Baseline Trail Making Test B (completed within 240 sec: yes/no)
- Use of ADM (Yes / No)
- Use of Anti-Chorea Medication (Yes / No)
- Use of Anti-Psychotic Medication (Yes / No)

The MMRM analyses will also be provided for change from baseline in primary endpoint within each baseline subgroup level. If any treatment group for any level of subgroup has  $\leq 10$  participants with available CFB at Day 84, the subgroup level will not be used in the analysis.

A forest plot of the difference in LS means and 95% CI bar for the changes from baseline to Day 84 on SDMT score overall and in each subgroup will be provided.

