#### 8.3.4. Analysis of Key Secondary Efficacy Variable

The key secondary efficacy endpoints are the change from baseline to Day 84 on 1) UHDRS- Independence Scale; 2) Trail Making B (TMT-B) in a subgroup of participants who were able to complete the test within 240 seconds at Baseline; 3) One Touch Stockings of Cambridge (OTS-MLC) ; 4) Paced Tapping Test (PTAP); 5) Huntington's Disease Everyday Functioning (Hi-DEF) – at home subdomain score; 6) Clinical Global Impression – Severity (CGI-S) – cognitive status subdomain score. These key secondary endpoints will be analyzed similarly to the analysis of primary endpoint.

Plot showing the LS means of key secondary endpoints  $\pm$  SE bar over time within each treatment group will be provided.

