### 8.3.5. Multiplicity Adjustment

The statistical comparisons for the primary efficacy endpoint and the key secondary endpoint will be carried out in the fixed-sequence procedure which tests hypotheses in a hierarchical order to control the familywise type I error rate. This means that statistically significant results for the comparison in the higher rank (primary) for no difference between SAGE-718 versus placebo is required to initiate the testing of the next comparison in the lower rank (key secondaries) for no difference between SAGE-718 versus placebo. Since a hierarchical procedure is used, each comparison will be tested at a significance level of 0.05 and an overall alpha level of 0.05 will be preserved. The hierarchical order for the key secondary outcomes is as follows: 1) UHDRS-Independence Scale; 2) Trail Making B (TMT-B) in a subgroup of participants who were able to complete the test within 240 seconds at Baseline; 3) One Touch Stockings of Cambridge (OTS-MLC) ; 4) Paced Tapping Test (PTAP); 5) Huntington's Disease Everyday Functioning (Hi-DEF) – at home subdomain score; 6) Clinical Global Impression – Severity (CGI-S) – cognitive status subdomain score.

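### The SAP's MMRM sample code fits by ML rather than REML, so the primary Day 84 standard error is about 1% too small, and about 6% too small in a subgroup at the smallest size allowed

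*SAP*

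**What the plan says.** SAP Section 8.3.3.1 sets out the primary model: change from baseline in SDMT, with treatment, visit, treatment-by-visit and baseline score as fixed effects and an unstructured (UN) covariance fitted in PROC MIXED. On inference it says "The Kenward-Roger correction to degrees of freedom will be applied". It also gives a convergence fallback sequence, with the rule "When the covariance structure is not UN, the sandwich estimator for the variance-covariance matrix will be derived". It names neither ML nor REML, and the protocol's efficacy section is also silent.

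The likelihood method is set explicitly in one place only, the MMRM sample code in SAP Appendix B: "proc mixed data=data method=ml". The same block requests Kenward-Roger and UN. The MMRM call in Step 5 of the control-based multiple imputation code, also in Appendix B, has no method option.

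The same model is used well beyond the primary test:

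- **Key secondary endpoints (8.3.4):** "These key secondary endpoints will be analyzed similarly to the analysis of primary endpoint".
- **Fixed-sequence testing (8.3.5):** "each comparison will be tested at a significance level of 0.05 and an overall alpha level of 0.05 will be preserved".
- **Subgroups (8.3.3.4):** the MMRM is refitted within each subgroup level. A level is dropped when either arm has 10 or fewer "participants with available CFB at Day 84, the subgroup level will not be used in the analysis". The smallest level analysed therefore has 11 per arm with Day 84 data. The subgroup estimates and their 95% intervals are then shown together in a forest plot.

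**The concern.** ML treats the fitted means and the baseline slope as known when it estimates the covariance matrix, so its variance estimates are biased low; REML allows for them. Kenward-Roger adjusts for the uncertainty in the estimated covariance and sets the degrees of freedom, but it does not undo the bias. With ML it also returned about three more degrees of freedom in the fits below. Both effects narrow the interval.

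At stake are the accuracy of the 0.05 level for the primary and key secondary tests, the coverage of the subgroup intervals, and comparability within the Section 8.3.3.3 forest plot. That plot shows the primary estimate beside the multiple-imputation estimate, and the SAP does not make sure that the two use the same estimator.

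**Working it through.** **Inputs from the documents.** SD of change 7.3, difference 4 points, two-sided alpha 0.05, 90% power, 71 evaluable per arm (SAP 5.2), and "Assuming a 20% dropout and a 1:1 randomization ratio, approximately 178 randomized participants (89 per treatment group) will be required". Modelled visits are Days 14, 28 and 84, as in the multiple-imputation code. The subgroup floor is 11 per arm (8.3.3.4).

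**Assumptions not in the documents.** Within-participant correlation 0.6 (range 0.4 to 0.8), baseline slope of -0.3 SD per SD, random monotone dropout, no treatment effect. The Kenward-Roger calculation was programmed independently of SAS.

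**1. The plan's own figure.** The noncentral t calculation gives power 0.896 at 70 per arm and 0.900 at 71, so 71 is right. 71/0.8 = 88.75, or 89 per arm and 178 in total. The sample size reproduces.

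**2. Closed form.** With p mean parameters estimated at a visit from N participants,

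SE(ML)/SE(REML) = sqrt((N - p)/N), and type I error = 2·P(t with N-p df > ratio × t(0.975, N)).

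Here p lies between 2 (two arm means) and 3 (plus a baseline slope). The slope is shared across visits, so the repeated-measures model falls between the two; with a single post-baseline visit p = 3 is exact.

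| N | p | SE ratio | Type I error |
|---|---|---|---|
| 142 | 2 | sqrt(140/142) = 0.993 | 0.0516 |
| 142 | 3 | sqrt(139/142) = 0.989 | 0.0525 |
| 71 | 3 | sqrt(68/71) = 0.979 | 0.0551 |
| 22 | 2 | sqrt(20/22) = 0.953 | 0.062 |
| 22 | 3 | sqrt(19/22) = 0.929 | 0.069 |

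**3. Simulation of the Appendix B model**, with ML and REML fitted to the same data:

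| Setting | Runs | SE ratio | Type I, ML | Type I, REML |
|---|---|---|---|---|
| 89 per arm, 20% dropout | 30,000 | 0.992 | 0.0513 | 0.0495 |
| 71 per arm, complete | 40,000 | 0.990 | 0.0524 | 0.0505 |
| 30 per arm | 20,000 | 0.977 | 0.0553 | 0.0507 |
| 20 per arm | 40,000 | 0.966 | 0.0616 | 0.0526 |
| 14 per arm, 11 at Day 84 | 40,000 | 0.944 | 0.0648 | 0.0496 |
| 11 per arm, correlation 0.4 | 80,000 | 0.939 | 0.0655 | 0.0501 |
| 11 per arm, correlation 0.6 | 80,000 | 0.937 | 0.0673 | 0.0501 |
| 11 per arm, correlation 0.8 | 80,000 | 0.934 | 0.0672 | 0.0494 |

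Coverage is 1 minus the rejection rate: at 11 per arm, 93.3% to 93.5% with ML against about 95.0% with REML. The 20-per-arm row carries simulation noise, since its REML rate is itself above 0.05. The t formula at ratio 0.966 gives about 0.0585, so coverage there is nearer 94.1% against 95%. Adding Day 112 as a fourth visit at 11 per arm leaves the ratio at 0.938. In the 89-per-arm design, correlations of 0.4 and 0.8 give ratios of 0.9915 to 0.9916.

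**4. Does Kenward-Roger rescue it?** No. In further fits the ML shortfall with and without the Kenward-Roger adjustment agreed to about 0.1 percentage point (6.33% against 6.28% at 11 per arm). Degrees of freedom there were 22.4 with ML and 19.5 with REML.

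**5. When would the primary verdict change?** Solving for the ML p-value at which the REML p-value is 0.05 gives 0.0478 (71 per arm, complete) and 0.0481 (89 per arm with dropout). In the latter design 0.18% of simulated trials were significant with ML only.

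**6. Key secondaries.** An endpoint with Day 84 as its only post-baseline visit and N = 142 has ratio 0.989 and type I error 0.0525. The size of the Trail Making B subgroup is not given. If half to all of 142 qualify (an assumption), the same formula gives 0.979 to 0.989.

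**The case against.** The best case on the other side is materiality. Every test that carries alpha is almost untouched: about 0.2 percentage points of type I error on the primary, with a change of verdict only in a sliver below p = 0.05. The 6% figure needs a subgroup level near the floor. The documents give no subgroup sizes, and subgroup intervals lie outside the testing hierarchy. All of this stands, and it is why the point is minor. Nor is 6% a strict upper limit: the mean shortfall reaches 6.6% at correlation 0.8.

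It can also be said that the code is labelled a sample, that Appendix B is visibly template code (it contains placeholders and misspelt variable names), and that Section 8.3.3.1 governs. Whether the line would be run unchanged is indeed an inference. But Section 8.3.3.1 is silent on the likelihood, so nothing overrides the code. A programmer who follows the SAP fits ML, and one who sets the sample code aside has no stated method.

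**Conclusion.** The specification is wrong as written, and the consequence is small. If the sample code is followed, the primary Day 84 standard error is about 1% too small (closed form 0.7% to 1.1%) and the test runs at 5.1% to 5.2%. Key secondaries carry a bias of the same order, so the SAP's claim to preserve 0.05 is very slightly untrue. At 11 participants per arm with Day 84 data the standard error is about 6% too small (5.6% to 6.6% across the simulated settings), and nominal 95% intervals cover about 93% to 94%.

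These figures rest on the assumed correlation, baseline slope and dropout pattern; varying the correlation barely moved them. They apply while the fit keeps UN under ML. They do not apply if the fallback reaches another structure, where the sandwich estimator takes over.

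**What to change.** In SAP Appendix B, change `method=ml` to `method=reml` in the MMRM code, and write `method=reml` explicitly in Step 5 of the multiple-imputation code. In Section 8.3.3.1, add one sentence stating that all MMRMs are fitted by REML. This should be done before unblinding, so that the estimator is not chosen with the results in view.

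The cost is two code edits and one sentence. Primary confidence intervals widen by about 1%, and the sample size is unaffected.
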